## **2. STUDY DESIGN**

This is a phase II non-randomized, open-label study in patients with moderate to severe cGvHD who have failed to respond to, or are intolerant of first line therapy. Patients will receive combination therapy with two oral agents (belumosudil, ruxolitinib) with documented individual efficacy as second line in cGVHD treatment. A maximum of 63 participants are expected to be enrolled in Canada.

[figure not shown]
Participants will begin on 10 mg BID of oral ruxolitinib alone for one cycle (i.e. Cycle 1). Each cycle is equal to 28 days. Starting at cycle 2, they will take belumosudil in addition to ruxolitinib, at a dose of 200 mg OD or 200 mg BID (if on a PPI). Patients will remain on dual therapy for 48 weeks (i.e. 12 cycles), until progression of cGVHD, or intolerance to either agent, whichever occurs sooner. A safety visit will be conducted at the end of treatment, 28 days following end of treatment, as well as a remote follow up visit conducted 24 weeks following end of treatment.

The end points will include overall response rates at 24 weeks on treatment and failure-free survival at 48 weeks on treatment (i.e., 28 and 52 weeks on combination therapy) which adopts composite endpoints including: (1) requirement of additional treatment or switch over, (2) progression or flare-up of GvHD with/without ruxolitinib tapering, and (3) death from relapse/non-relapse mortality.

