### **2.1 Estimated Study Duration**

The enrollment period of the study is expected to be approximately 12-18 months. The screening period may last up to 14 days. The treatment period for an individual patient is expected to be approximately 52 weeks from the date of starting therapy (i.e., Cycle 1 Day 1). Patients will be followed for evidence of progression of cGVHD, survival, and unexpected toxicity (if any) for 24 weeks after the end of treatment visit.

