## 5. STUDY TREATMENT

### 5.1 Study Drug Administration

The Investigational Medicinal Product (IMP), Belmosudil, will be provided by Sanofi as 200 mg tablets.

Ruxolitinib will be dispensed as either 5 or 10 mg tablets, and will be obtained through the site's local pharmacy, as it will be administered per SOC.

All patients will receive open-label IMP. Responsibility for treatment of patients rests with the QI. Prior to initiating ruxolitinib (Cycle 1 Day 1), a tuberculosis skin test or interferon-gamma release assay should be performed in accordance with the approved JAKAVI® (ruxolitinib) product monograph to screen for latent tuberculosis infection, with results interpreted cautiously in immunocompromised patients. Positive results should prompt appropriate evaluation and management per institutional guidelines before starting isoniazid therapy. If the patient had been already treated with isoniazid prophylaxis for 6 months due to prior history of tuberculosis skin test or interferon-gamma release assay, this test will be exempted.

Eligible participants in this study will be started on ruxolitinib monotherapy orally at the standard recommended dose of 10 mg BID for 4 weeks (28 days). After one full cycle of ruxolitinib treatment (i.e., C2D1), the participant will have an AE assessment and, unless Grade  $\geq 3$  AE is observed, will continue on the same dose of ruxolitinib **plus** oral belumosudil 200 mg QD (or BID if receiving concomitant PPI) starting on C2D1.

In the event that the participant is experiencing Grade  $\geq 3$  AE(s) at the intended C2D1 visit assessment, treatment with belumosudil should not begin. This visit will be considered an unscheduled visit and the C2

D1 visit should be rescheduled. The participant can continue on ruxolitinib alone and should be followed for resolution of the Grade  $\geq 3$  AE(s). If the Grade  $\geq 3$  AE(s) improves to Grade  $\leq 2$  or resolves completely within 4 weeks, the participant will still be eligible to receive belumosudil. In this case, they should come back in for a true C2D1 visit and can complete all the necessary assessments as well as belumosudil dosing. If the Grade  $\geq 3$  AE(s) does not recover within 4 weeks, the participant will complete the End of Treatment visit and discontinue study. If there are any questions or concerns about the patient status and treatment in these scenarios, this should be discussed with the sponsor.

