### Missed Belumosudil with BID Scheduling

- For patients taking belumosudil on a BID dosing schedule, if a morning or evening dose is delayed for less than 6 hours of time, the dose should be

taken as soon as possible. The patient should then take the next dose as planned, resuming the regular dosing schedule.

- If a morning or evening dose is delayed for more than 6 hours of time, the patient should skip this dose and resume dosing with the next dose as per the original schedule in order to prevent overdosing.

Note that if the patient skips more than 7 consecutive days of both belumosudil and ruxolitinib, the patient should be discontinued from the study unless approved by the sponsor and treating Investigator.

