#### **Belumosudil**

Table 1 and 2 below outlines the instances where belumosudil dose reductions are recommended as well as the corresponding recommended dose reduction.

**Table 1.** Guideline for management of treatment-emergent toxicities

Toxicity	Recommended Action
Grade $\geq 3$ LFTs (AST, ALT or total bilirubin)	

• Hold Belumosudil dosing until resolution to Grade 1 or below levels

• Consider resuming Belumosudil after resolution to Grade 1 or below levels. If resuming, then resume at one dose decrement

	
 
If toxicity (Grade <math>\geq 3</math>) recurs, discontinue Belumosudil
 

Other Grade $\geq 3$ clinically significant toxicities considered related to Belumosudil	
 
Hold Belumosudil dosing until toxicity has resolved to Grade 1 or below levels. If resuming Belumosudil after resolution to Grade 1 or below levels, then resume at one dose decrement
 
If toxicity recurs, hold dose as above then consider resuming Belumosudil at one dose decrement
 

Dose interruption for up to 14 days for toxicity management is permitted. Patients requiring pauses of more than 14 days will be discontinued from the study unless approved by the Sponsor.

**Table 2.** Belumosudil Dose Decrements

Belumosudil Dose	Dose Reduction
200mg BID	200mg QD
200mg QD	200mg QOD

If the reduced dose is tolerated for 1 complete cycle, the dose may be re-escalated to the previous dose.

In practice, when overlapping toxicities occur (most commonly cytopenias, liver function test abnormalities, or infections), the treating physician will exercise clinical judgment to prioritize dose modification based on the dominant contributing agent, severity of the toxicity, and organ-specific involvement. As a general guiding principle:

- For hematologic toxicities (e.g., thrombocytopenia, neutropenia): ruxolitinib will be dose-reduced or interrupted first, as it is the primary agent associated with JAK2-mediated cytopenias, per the product monograph.
- For liver function test elevations (e.g., bilirubin, ALT/AST): belumosudil will be dose-reduced or interrupted first, consistent with its dose modification tables (Table 1 and Table 2), unless the QI determines ruxolitinib is the more likely contributor based on timing and clinical context.

**Table 3.** Dose modification for clinically relevant hematologic side effects

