### **5.5 Patient Compliance and Dropout**

To the extent possible, patients must strictly follow the continuous daily dosing schedule during the course of study treatment. Patients that skip more than 7 consecutive days of both drugs, in the absence of investigational product related toxicity, will be discontinued from the study unless approved by both the Sponsor and treating Investigator.

Compliance to study medication dosing will be documented using patient diaries and pill counting. Patients will record the date, time and number of pills consumed in the diary on a daily basis. The Principal Investigator (PI) or designee will account for the number of tablets dispensed against those returned by the patient. Any deviations and missed doses will be recorded in the eCRF and drug accountability logs. Reasoning for missed doses should be documented in the patient diaries when possible, as well as within the study drug administration form in the eCRF. The PI / designee will try to ensure complete compliance with the dosing schedule by providing timely instructions to the patients.

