### **5.6 Premature Withdrawal/Discontinuation Criteria**

At the discretion of the QI, a patient may be removed from the study for the following reasons:

- Progression of cGVHD as defined by NIH Consensus Criteria
- Noncompliance with study procedures
- Need for treatment with medications, such as a new systemic agent for cGVHD, not allowed by the study protocol
- Recurrence of underlying malignancy, as defined by established disease specific criteria, or other intercurrent illness that interferes with study assessments

- Unacceptable toxicity related to study participation
- Investigator decision.
  - Note that patients should be withdrawn from the study if there has been no response after 12 months of treatment, if in the judgement of the Investigator there has been no clinical benefit for the patient, e.g., in terms of organ score improvements, improvements in Lee symptom scores or reductions of corticosteroid / tacrolimus doses.
- Other treatments become available
- Patient preference / withdrawal of consent or loss to follow-up
- Termination of the study by the sponsor
- Pregnancy in a female participant will lead to definitive treatment discontinuation in all cases.

Patients with a Lack of Response or Mixed response may continue treatment with belumosudil and ruxolitinib, and can remain on study if the treating Investigator considers continued treatment to be in the patient's best interest, but only after approval from the Sponsor and documentation of patient's willingness to continue. The rationale for continued treatment in such instances must be clearly documented. For clarity, Lack of Response or Mixed response will be considered as progression event for analysis purposes.

Patients may withdraw from the study at any time. Patients who discontinue from the study will be encouraged to return to the study site to undergo the evaluations listed for the End of Treatment Visit and for follow-up visits. In the instances where a reason for withdrawal of consent is given, this will be captured in the eCRF. Patient data up to withdrawal of consent will be included in the analysis of the study, and where permitted, publicly available data can be included after withdrawal of consent.

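### Section 5 takes patients off the study for toxicity, dosing pauses and missed doses and leaves most follow-up voluntary, contradicting the 24-week follow-up set elsewhere and putting the secondary FFS estimate at risk

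*Protocol*

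**What the plan says.** **Leaving the study (Protocol Section 5).**
- Section 5.1, repeated in the notes to the Section 8 calendar: if a Grade 3 or higher AE at the intended C2D1 visit has not recovered within 4 weeks, "the participant will complete the End of Treatment visit and discontinue study".
- Section 5.2: "if the patient skips more than 7 consecutive days of both belumosudil and ruxolitinib, the patient should be discontinued from the study", unless the sponsor and treating investigator approve otherwise.
- Section 5.3: "Patients requiring pauses of more than 14 days will be discontinued from the study unless approved by the Sponsor".
- Section 5.5: patients who miss more than 7 consecutive days of both drugs, without product-related toxicity, "will be discontinued from the study unless approved by both the Sponsor and treating Investigator".
- Section 5.6: noncompliance and unacceptable toxicity are among the reasons for which the investigator may remove a patient from the study. For the End of Treatment (EOT) and follow-up evaluations, "Patients who discontinue from the study will be encouraged to return to the study site". On data use, "Patient data up to withdrawal of consent will be included in the analysis of the study".

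**Follow-up after treatment (elsewhere in the Protocol).**
- Section 2.1, and the Synopsis in the same terms: "Patients will be followed for evidence of progression of cGVHD, survival, and unexpected toxicity (if any) for 24 weeks after the end of treatment visit".
- Section 8: a 28-day safety visit, then a 6-month contact that may be by phone and records survival and new cGvHD therapy.
- Section 9: cGvHD therapies started in those 24 weeks are captured, and a new systemic one is a study treatment failure.
- Section 10.7: everyone who stops protocol treatment is followed for toxicity and seen about 28 days later.

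**The FFS endpoint.** Section 2 lists "1) requirement of additional treatment or switch over" as a failure component and attaches no cause to it. Section 11.3.1 ties a switch to GvHD progression or loss of response. It names the Kaplan-Meier method, with rates at weeks 28 and 52, and gives no censoring rule.

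**The concern.** Being taken off drug for toxicity, a long pause, missed doses or noncompliance is not itself an FFS event. The event, if there is one, is a later switch, progression, relapse or death. These patients have lost the study treatment for their cGvHD, so they are plausibly more likely than others to start another systemic agent. If they leave the study at that moment and their return is optional, the later event may never be recorded.

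Kaplan-Meier treats a censored patient as having the same later risk as those still observed. If removed patients have a higher risk, censoring them at removal is informative and pushes FFS upward. How to censor can be settled in an analysis plan. Whether the events are collected at all is settled in the protocol, and data not collected cannot be recovered afterwards.

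**Working it through.** **1. The passages side by side.**

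| Question | Section 5 | Elsewhere in the protocol |
|---|---|---|
| What ends? | The study (5.1, 5.2, 5.3, 5.5, 5.6) | Protocol treatment (10.7) |
| EOT visit? | Required after unresolved C2D1 toxicity (5.1, 8); otherwise encouraged (5.6) | In the calendar (8) |
| Follow-up after EOT? | Encouraged (5.6) | Will take place for 24 weeks (Synopsis, 2.1) |
| Later cGvHD therapy? | Not addressed for those removed | Captured (8, 9) |

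The two columns cannot both guide a site. The defect is a contradiction, not an absence of planned follow-up.

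**2. Possible size.** The protocol gives no FFS rate, removal rate or switch rate, so there is no figure of its own to reproduce. Assumptions:
- F = 60% or 70%: 52-week FFS without removals (exponential failure times).
- d = 5%, 10% or 20%: share removed, at a uniform time in weeks 4 to 40. The 10% equals the dropout allowance in Section 11.1.
- s = 50% or 100%: share of those removed who switch, within 12 weeks. Each switch counts as failure.

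Every switch then falls by week 52 (40 + 12 = 52), so:
- true FFS at week 52 = F × (1 − d × s)
- Kaplan-Meier censored at removal estimates F
- overstatement = F × d × s

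Results at week 52:
- Smallest: 0.60 × 0.05 × 0.5 = 0.015, or 1.5 points.
- 10% removed: from 0.60 × 0.10 × 0.5 = 0.03 to 0.70 × 0.10 × 1 = 0.07, or 3 to 7 points.
- Largest: 0.70 × 0.20 × 1 = 0.14, or 14 points.

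A simulation of 300,000 patients per scenario agrees. Three of its scenarios:

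| F | d | s | True, week 52 | Censored at removal | Followed 24 weeks |
|---|---|---|---|---|---|
| 60% | 5% | 50% | 58.4% | 59.9% | 58.4% |
| 70% | 10% | 100% | 63.0% | 69.9% | 63.0% |
| 70% | 20% | 100% | 56.0% | 70.0% | 56.0% |

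At week 28 the overstatement is about 1 to 8 points over all scenarios, and 2 to 4 points at 10% removed. When the 24-week follow-up is carried out, the estimate matches the true value to within 0.1 point in every scenario. That rests on switches coming within 12 weeks of removal.

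For scale, the 95% CI half-width with 63 patients, ignoring censoring, is 1.96 × √(0.70 × 0.30 / 63) = 11.3 points, or 1.96 × √(0.60 × 0.40 / 63) = 12.1 points.

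**3. Does 24 weeks reach the landmark?** A patient removed in week r has planned contact to week r + 24, and r + 24 < 52 whenever r < 28. A C2D1 toxicity removal comes at about week 4 + 4 = 8, so contact ends near week 32, about 20 weeks short of week 52.

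**The case against.** A reader might infer that the protocol censors these patients and that FFS is therefore overstated. The documents do not support that. No censoring rule is stated, an analysis plan may supply one, and Section 5.6 limits data use only at withdrawal of consent. A reader might equally infer that there is no follow-up after removal. That is also wrong: the Synopsis and Sections 2.1, 8, 9 and 10.7 provide for it, and with it the bias is near zero under the stated assumptions.

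Other points on that side are fair:
- Section 5.1 requires the EOT visit after unresolved C2D1 toxicity.
- The pause and missed-dose rules can be waived, the missed-dose rule needs both drugs skipped, and removal under Section 5.6 is discretionary.
- The encouragement sentence directly follows one on patients' freedom to withdraw, so it may have been meant for patient-initiated withdrawal, where no stronger wording would be proper.
- Under Section 11.3.1 a switch for toxicity alone may not count as failure even when observed, so some of the assumed events may not apply.
- The rates are all assumed. The bias is below the CI half-width in most scenarios, and FFS is secondary with no stated test or threshold.

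What remains is the contradiction. The encouragement sentence covers all who discontinue from the study, which is the very status that Sections 5.1 to 5.5 assign. Section 5.6 and Section 10.7 require follow-up of the AE when an AE is the reason for leaving, but that does not secure later therapy, relapse or death. Even under the narrower Section 11.3.1 definition, progression, relapse or death after removal could be missed.

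**Conclusion.** The point holds as a contradiction in the protocol with a conditional consequence. Section 5 removes patients from the study for treatment-related reasons and makes most later visits optional, while other sections say they will be followed. If sites act on Section 5 and the patients are lost and censored, the secondary FFS estimate would probably be too high. Under the assumptions shown, the excess is about 1.5 to 14 points at week 52, or 3 to 7 at 10% removed. These figures assume that every removed patient is lost at removal and that every switch counts, so they are upper values for each set of rates. With follow-up carried out and switches within 12 weeks, the excess is near zero.

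The primary ORR test is not affected by this route. Two related weaknesses stand whichever way Section 5 is read: 24 weeks after EOT does not reach week 52 for anyone removed before week 28, and Sections 2 and 9 disagree with Section 11.3.1 on whether a switch without progression or loss of response is a failure. A change is worth making because it is cheap now and the lost data could not be recovered later.

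**What to change.** Leave the treatment-stopping rules as they are; whether they are right is not judged here. Then:

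1. In Sections 5.1, 5.2, 5.3, 5.5 and 5.6, and in the matching calendar note in Section 8, replace removal from the study with discontinuation of study treatment.
2. State that all such patients complete the EOT visit, the 28-day visit and the 6-month contact, and are also contacted for progression, new systemic cGvHD therapy, relapse and death to at least week 52 from C1D1.
3. State that only withdrawal of consent for follow-up, loss to follow-up, death or study termination ends participation. Keep the encouragement wording for patients who choose to withdraw.
4. Reconcile the FFS failure definition across Sections 2, 9 and 11.3.1, so that it is clear whether a switch made for toxicity counts.

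Cost: a wording amendment. The visits are already in the calendar, and the added burden is a few remote contacts for patients who stop treatment early.

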### **5.7 Patient Replacement**

Enrolled participants withdrawn from the study before receiving any study drug will be replaced.

### **5.8 Data Safety Monitoring Board (DSMB)**

An independent Data Safety Monitoring Board (DSMB) will be established for this study. The DSMB will comprise of experts in stem cell transplantation and the management of

GVHD, independent of the study. A list of the DSMB members can be found in the DSMB charter.

The DSMB will monitor the safety aspects of the trial and will review safety data on a bi-annual basis. Additional meetings may be scheduled as necessary and if any of the safety stopping rules indicated below are met. Please refer to the DSMB charter for additional details.

## **5.9 Safety Stopping Rules**

Accrual will be on hold and a meeting held with the PI, investigators and Data Safety Monitoring Board (DSMB) if the following occurs:

1. If there is a death or unacceptable toxicity (SAE Grade  $\geq 4$ ) attributed as: possibly, probably or definitely related to the study drug.
2. If the first 3 patients enrolled experience significant toxicity (i.e. Grade  $\geq 3$  AEs lasting 4 weeks or longer) attributed as: possibly, probably or definitely related to the study drug.

A decision will be made by the Sponsor and DSMB regarding whether the study will be re-opened for the next patient in the study or not. If there is disagreement in the SAE causality assessment or whether or not to re-open accrual between the different parties, the final decision will rest on the DSMB. Ozmosis will notify all sites and applicable parties on the decision and whether accrual has re-opened. Only when it is deemed safe can the next patient start the treatment phase of the study.

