--	--

	
13. Patients with known active CNS disease (malignant involvement of CNS).
 
14. Patients with active acute GvHD grade III-IV.
 
15. History or other evidence of severe illness or any other conditions that would make the patient, in the opinion of the treating Investigator, unsuitable for the study (such as malabsorption syndromes, poorly controlled psychiatric disease or coronary artery disease).
 
16. Known hypersensitivity to belumosudil, ruxolitinib or any of their excipients
 
17. Patients unable to swallow oral medications
 
18. Female participants who are pregnant or breastfeeding

Patient Screening Assessments:	
 
• Written Informed Consent
 
• Inclusion/Exclusion Criteria
 
• Demographics
 
• Medical History & Prior GvHD Treatments
 
• Physical Examination (includes height and weight) & ECOG performance status assessment
 
• Vital Signs
 
• 12-lead ECG
 
• Urine pregnancy test in biologically female patients
 
• Hematology
 
• Serum Chemistry
 
• Virology
 
• Concomitant Medications
 
• Correlative Sampling (optional)
 
• P-ROM (Photographic Range-Of-Motion) assessment
 

Treatment and Post-Treatment Assessments:	
Assessments to be completed on visits as per the Study Calendar
 
Treatment Phase (0, 2, 4, 6, 8, 16, 28, 40, 52 weeks)
 
 
• Physical Examination & ECOG performance status assessment
 
• Vital Signs
 
• Hematology
 
• Serum Chemistry
 
• AE Assessment if required
 
• Ruxolitinib and belumosudil administration
 
• Concomitant Medications
 
• NIH consensus based GvHD organ specific score and global severity score (i.e. mild vs moderate vs severe grade)
 
• NIH consensus based GvHD response assessment
 
• Modified Lee Symptom Scale
 
• P-ROM (Photographic Range-Of-Motion) assessment
 
• Serum pregnancy test in biologically female patients
 
• Pulmonary Function Test
 
• IP return and accountability
 
• Correlative Samples (as per the Study Calendar, optional)
 

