There are no prospective studies that have examined the combination of two, non-first line agents in the setting of cGvHD. Therefore, this open-labelled study aims to look at the outcome of combination therapy in an underserved population that is affected by the dual stressors of cGvHD as well as the complications of therapy. There are no uniformly used, nor centrally approved second-line treatments following corticosteroid resistance in cGvHD. Also, practices vary as to the selection of various systemic therapies since to date, no improvement in the high mortality rates has been documented despite treatment with these agents.

Both agents are known to be effective in managing cGVHD but can differ with respect to time to response and mechanisms of action. Ruxolitinib demonstrates efficacy relatively faster due to its anti-inflammatory mechanisms and is therefore useful in mitigating the initial inflammatory processes seen at the onset of cGvHD. It however, does not seem to impact established fibrotic forms of cGvHD to the same degree as belumosudil, which by virtue of its unique mechanism of action, is the only agent currently available that has shown improvement in the organs affected by fibrosis as sequelae of cGvHD. This effect can take longer to establish (as long as 3-6 months) leading to the need for longer durations of steroid or other immunosuppressive therapy. Combining both agents is therefore expected to provide rapid control of the inflammatory process through the use of ruxolitinib and allow sufficient time for the antifibrotic effect of belumosudil to be established leading to better disease control overall without exposing the patient to high doses or prolonged courses of steroids or immunosuppression.

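### The Section 5.9 safety hold stops new patients starting ruxolitinib but does not pause the first belumosudil dose at C2D1 for patients already in the lead-in

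*Protocol*

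**What the plan says.** Section 5.9 sets two triggers. One is a death or Grade 4 or higher SAE at least possibly related to study drug. The other is prolonged Grade 3 or higher related toxicity in the first three patients. When either is met: "Accrual will be on hold and a meeting held with the PI, investigators and Data Safety Monitoring Board (DSMB"). The Sponsor and DSMB decide whether to re-open for the next patient, and "Only when it is deemed safe can the next patient start the treatment phase of the study". Section 5.8 links the board's extra meetings to these rules ("Additional meetings may be scheduled as necessary and if any of the safety stopping rules indicated below are met") and refers to the DSMB charter for details.

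The synopsis places the start of treatment at week 0: "Treatment Phase (0, 2, 4, 6, 8, 16, 28, 40, 52 weeks"). At that visit the patient starts ruxolitinib alone.

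Belumosudil enters at C2D1. Section 5.1 says: "After one full cycle of ruxolitinib treatment (i.e., C2D1), the participant will have an AE assessment and, unless Grade" 3 or higher toxicity is observed, belumosudil is added. A patient with such an event stays on ruxolitinib. If it improves in time, "they should come back in for a true C2D1 visit"; if it "does not recover within 4 weeks, the participant will complete the End of Treatment visit and discontinue study". The study calendar footnote repeats this rule. Neither place mentions a study-level hold.

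**The concern.** The study-level gate and the investigational exposure are four weeks apart. The hold stops a new patient from starting a standard-of-care drug. It does not stop a patient who is already in the lead-in from taking a first dose of the drug under study.

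The events that trigger a hold are those for which the first combination dose matters most: a death or Grade 4 or higher SAE that may be related to belumosudil or to the pairing. Section 1.2 describes the evidence base: "There are no prospective studies that have examined the combination of two, non-first line agents in the setting of cGvHD". The protocol itself treats C2D1 as the key exposure, since it puts a patient-level safety check there and defines the Safety population by receipt of belumosudil.

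**Working it through.** The protocol states no figure on this point, so the check is a comparison of the rules followed by an illustration of scale.

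**Comparison of the rules**

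| Step | Week | Drug started | Written gate |
|---|---|---|---|
| C1D1 | 0 | Ruxolitinib (standard of care) | Eligibility; the Section 5.9 hold |
| C2D1 | 4 | Belumosudil added | The patient's own Grade ≥3 AE (Section 5.1) |

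Section 5.9 names accrual and the next patient. Section 5.1 names the individual's adverse event. No sentence joins the two, so a well patient in the lead-in proceeds.

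**Inputs.** 63 patients (Section 2) enrolled over 12 to 18 months (Section 2.1), with a 4-week lead-in (Section 5.1). Assumed: uniform accrual, nobody stopping in Cycle 1, nobody already deferred for their own event, and every site dosing on schedule. The protocol does not give the hold length *h*, so a range is shown.

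**Accrual rate**
- 12 months = 52.18 weeks: 63 / 52.18 = 1.21 patients per week.
- 18 months = 78.27 weeks: 63 / 78.27 = 0.80 patients per week.

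**Patients reaching C2D1 during a hold** = rate × min(*h*, 4). The cap at 4 weeks applies because no new patient enters the lead-in once accrual stops. The last column is 1 − exp(−mean), assuming Poisson arrivals.

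| Hold | Expected patients | Share of 63 | Chance of at least one |
|---|---|---|---|
| 1 week | 0.80 to 1.21 | 1.3 to 1.9% | 55 to 70% |
| 2 weeks | 1.61 to 2.41 | 2.6 to 3.8% | 80 to 91% |
| 4 weeks or more | 3.22 to 4.83 | 5.1 to 7.7% | 96 to 99% |

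**When it can arise.** From first enrollment to 4 weeks after the last: 52.18 + 4 = 56.2 weeks to 78.27 + 4 = 82.3 weeks. In the final 4 weeks an accrual hold stops nobody, while 3.2 to 4.8 patients are still in the lead-in at the start of that period, falling to none by its end.

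**The case against.** The strongest reply is that this is silence and not an error. Sections 5.9 and 5.1 do not contradict each other: one governs entry, the other an enrolled patient's progress. Holding accrual while a board considers patients on study is a recognised design, and Section 5.9 is equally silent on patients already taking the combination. The DSMB charter may deal with on-study patients.

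There are also real safeguards. Section 5.1 makes the Qualified Investigator responsible for treatment. SAEs go to the CRO within 24 hours (Section 10.8) and on to the Sponsor within a further 24 (Section 10.10). Investigators attend the hold meeting, each patient has an AE assessment at C2D1, Section 17.1 allows departures for an immediate hazard, and the Sponsor may stop the trial (Section 17.3). Belumosudil has been approved in Canada since March 2022 after at least two prior lines, and Section 1.3 cites real-world use of the pairing without significant toxicity or interaction problems.

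Most of this stands and limits the point. It does not close it. The safeguards are discretionary or indirect, and none requires a pause. Sites work from the protocol, so a charter rule would still need to appear there. Starting a drug during an unresolved safety review is also a different decision from continuing one.

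A reader might infer that lead-in patients would certainly be escalated by unaware sites, or that the percentages above are risks of harm. The documents support neither. The percentages are conditional on a hold occurring and on every site proceeding, the protocol gives no probability or length for a hold, and nothing here estimates excess harm.

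**Conclusion.** The point holds in a limited form. As written, the hold covers accrual and new C1D1 starts but not the first belumosudil dose at C2D1. If a hold occurs during accrual or within 4 weeks after the last enrollment, roughly 1 to 2 patients (1- to 2-week hold), and at most about 3 to 5 (4 weeks or more), could start the combination before the Sponsor and DSMB decide.

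These counts rest on uniform accrual and no discretionary deferral. They fall if early accrual is slow, if patients stop in Cycle 1, or if the second trigger fires when few patients are in the lead-in. They would rise slightly if some patients' C2D1 were already deferred for their own event.

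It would go too far to say that the trial has no procedure for these patients, since the charter is not shown, or that the combination is known to be unsafe. This is a gap in a safety rule that is worth closing.

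**What to change.** In Section 5.9, with a cross-reference in Section 5.1 and a matching line in the DSMB charter, state that:

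- during a hold, no patient takes a first dose of belumosudil unless the DSMB permits it, for example when the event is attributed to ruxolitinib alone (Section 10.3 already records attribution for each drug);
- lead-in patients continue standard-of-care ruxolitinib, and C2D1 is rescheduled by the mechanism already in Section 5.1;
- the DSMB decision explicitly covers lead-in patients and sets the longest allowed deferral, in place of the 4-week limit that applies to an individual's adverse event.

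The third item is needed because lifting the 4-week limit without a replacement would leave ruxolitinib monotherapy open-ended.

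The drafting cost is a few sentences. The clinical and analytic costs fall on the same few patients:

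- Belumosudil is delayed, and Section 1.2 says its effect can take 3 to 6 months.
- Ruxolitinib monotherapy before C8D1 is longer. With cycles counted from the rescheduled C2D1, C8D1 falls six 28-day cycles (24 weeks) later, so a 2-week deferral moves it from week 28 to week 30. Response is still judged against C1D1 (Section 7.2), so the primary response in these patients reflects a longer lead-in.
- Anyone who stops during the deferral stays in the ITT population but enters neither the Safety nor the Efficacy population (Section 11.2).
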